### **Safety Analysis**

All subjects in the study at will be included in the safety analysis. The frequencies of adverse event (AE) by type, body system, severity and relationship to study drug will be summarized. Serious adverse events (SAE), if any, will be described in detail. AE incidence will be summarized along with the corresponding exact binomial 95% two-sided confidence intervals.

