## 2.5. Randomized intervention

The randomized intervention will be: (1) fenofibrate (or its active metabolite, fenofibric acid) administered for 10 days (see **Appendix 3** for specific preparations and dosing), with appropriate dose reductions or exclusions will be implemented for patients with chronic kidney disease as per the approved preparation label; (2) Placebo of similar appearance (1:1 ratio). These interventions will be added to usual care. Participants and investigators (including research team members who administer the Dyspnea Borg scale and symptoms questionnaires) will be blinded to the randomized intervention. Primary analyses will be performed on an intent-to-treat basis.

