## 4. ADVERSE EVENTS

### 4.1. Adverse Event Reporting

Adverse events (AEs) will be captured in our data entry tool (RedCap). The DSMB will examine data periodically in order to compare the incidence of adverse events in both arms. Expedited reporting of individual AEs (within 48 hours of discovery by site investigators) will be required for severe AEs that are unexpected and felt to be probably or definitely associated with the study intervention. Such expedited reporting of AEs will be done from site investigators to the University of Pennsylvania study team, and the study team will in turn communicate these to the DSMB.

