#### Classification of Adverse Events for Causal Relationship to the Study Intervention

---

Not related or unlikely related	There is not a reasonable causal relationship to the investigational product and the adverse event, or there is a low likelihood that a causal relationship exists.
Probably or definitely related	There is reasonable or definite evidence to suggest a causal relationship between the drug and adverse event.

---

The events will be classified as serious or non-serious adverse events:

*Serious Adverse Events (SAE)* are adverse events, in which the investigator or sponsor believe that any of the following outcomes occur:

- Death
- Life-threatening AE: Places the participant at immediate risk of death at the time of the event as it occurred. It does not include an AE that, had it occurred in a more severe form, might have caused death.
- Persistent or significant incapacity or substantial disruption of the ability to conduct normal life functions.
- Inpatient hospitalization or prolongation of hospitalization.
- Important medical events that may not result in death, be life threatening, or require hospitalization may be considered a serious adverse event when, based upon appropriate medical judgment, they may jeopardize the participant and may require medical or surgical intervention to prevent one of the outcomes listed in this definition above.

Expectedness: Expected AEs will be those that are reported to be associated with COVID-19.

The following AEs are expected, disease-related events in patients with COVID-19

1. Arrhythmias, including ventricular arrhythmias and atrial fibrillation.

2. Acute coronary syndromes with or without coronary stenoses on coronary angiography
3. Myocarditis or worsening cardiac function.
4. Shortness of breath, pneumonia, acute respiratory distress syndrome and respiratory failure.
5. Fever, malaise and myalgia.
6. Worsening cognitive function.
7. Limb ischemia, coagulopathy, thrombosis, embolus.
8. Hypotension or hypertension.
9. Diarrhea, nausea, or vomiting.
10. Anosmia (loss of sense of smell).
11. Leukopenia or leukocytosis, thrombocytopenia.
12. Worsening renal function (resulting in various electrolyte abnormalities).
13. Worsening liver function.
14. Death.

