## 7. STATISTICAL CONSIDERATIONS

### 7.1. Power calculations

We will enroll 700 participants. Participants will be randomized to one of 2 interventions (fenofibrate plus usual care vs. placebo plus usual care). Assuming feasible distributions of participants across each of the five hierarchies from the available published evidence, we performed 10,000 simulations of rank distributions of 700 participants, and determined that there will be 80% power at an alpha of 0.0492 (allowing for one interim analysis at 50% of enrollment with an alpha of 0.0054) to observe an 11% difference in median rank scores between the treatment arms. Power calculations were performed using python and PASS16.

Enrollment of 700 participants will increase our power for secondary outcomes. For the secondary outcome of number of days alive, out of the intensive care unit, free of mechanical ventilation (invasive and non-invasive), extracorporeal membrane oxygenation (ECMO) or maximal available respiratory support in the 30 days following randomization, assuming a standard deviation of 7 (the SD from the REPLACE COVID trial for this outcome), a sample size of 700 would have 90% power to estimate a 1.7 day mean difference between treatment arms. Assuming that the SD may be higher in the current study with the inclusion of outpatients, we would have a sufficient power to estimate a 3.4 day mean difference between treatment arms with a SD of 14.

For the secondary outcome of the WHO ordinal scale, based on the ordinal scale distributions from the Remdesivir trial, we would have 90% power to observe an OR of 1.5 for clinical improvement in the ordinal scale. Given the expected lower severity of illness in our participants, with an adjusted reasonable distribution towards the lower end of the scale, we would have 90% power to observe an OR of 1.7.

For the exploratory outcome of all-cause death, assuming a death rate of 14% (observed in REPLACE COVID), we would have sufficient statistical power to detect a HR of 1.4. Considering the mixed inclusion of inpatients and outpatients, if the death rate is 5%, we would have sufficient statistical power to detect a HR of 1.7.

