### 7.2. Data Analysis Plan

The sample, both the baseline characteristics and the outcomes, will be explored and described using graphical techniques and summary statistics (means, medians, proportions and measures of variability) as appropriate. The initial description will consider the sample as a whole as well as by treatment arm.

The primary outcome variable will be the global rank score, as used previously in several similar randomized controlled trials to facilitate evaluation of composite outcomes of binary and continuous findings accounting for censorship for death. The predictor of interest for all outcomes will be randomized intervention (fenofibrate vs. control), with analyses based upon the total number of randomized participants. Initial descriptive estimates of all measures will be generated for study participants by treatment group. Statistics will include estimates of central tendency, measures of variability, and derived moments of skewness and kurtosis. Analyses of distributional properties will be performed to determine if variance stabilizing or normalizing transformations should be applied. Outliers will be assessed via visual inspection of distributions and checked for accuracy. Additionally, the intervention groups will be compared using Fisher's Exact tests.

The primary and secondary outcomes will be analyzed using a two-sided Wilcoxon rank sum test. Estimation, and 95% confidence intervals, of the differences between arms will be based on the Hodges-Lehman median difference as well as the Mann-Whitney Parameter, the probability that a subject from the fenofibrate arm has a score greater or equal to that of a subject for the control. This will be followed by a more comprehensive linear regression analysis allowing for assessments of the treatment effect on each continuous outcome of interest while controlling for effects of covariates including age, sex, inpatient vs. outpatient status at enrollment,  $\text{FiO}_2/\text{SpO}_2$  at the time of enrollment, ethnicity, body mass index, altitude above sea level and history of diabetes at baseline.

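### The SAP safety section specifies neither adverse-event tables by arm nor any between-arm estimate, only exact intervals for single proportions

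*SAP*

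**What the plan says.** The SAP's Safety Analysis section is one short paragraph. It covers all subjects and states that "The frequencies of adverse event (AE) by type, body system, severity and relationship to study drug will be summarized". Serious AEs are to be described in detail, and "AE incidence will be summarized along with the corresponding exact binomial 95% two-sided confidence intervals". Nothing in the paragraph says the tables are by arm, although the SAP does say so for descriptive statistics, the Cox models and non-adherence.

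The protocol bears on the point in four places:

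- Section 4.1: "The DSMB will examine data periodically in order to compare the incidence of adverse events in both arms". No method is given.
- Section 4.3: a list of 14 items introduced by "The following AEs are expected, disease-related events in patients with COVID-19". It includes worsening liver function, worsening renal function, myalgia and blood-count changes.
- Section 7.2: "Additionally, the intervention groups will be compared using Fisher's Exact tests". The variables are not named.
- Section 8.2: raised transaminases, creatinine and creatine kinase, rare rhabdomyolysis, and changes in blood counts are described as possible effects of fenofibrate.

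The SAP also compares all-cause death, and hospitalization of participants enrolled as outpatients, between arms by Cox model (Secondary Analysis, time-to-event outcomes).

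**The concern.** Several events of interest for fenofibrate are also caused by COVID-19. For these, the incidence in one arm, however precise, mixes drug and disease. The investigator's rating of relationship to study drug does not resolve this, because the disease always offers another explanation. The blinded 1:1 placebo arm does, but the written safety analysis contains no statistic that uses it.

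If AE tables carry only separate intervals, readers will tend to judge harm by whether the intervals overlap. That is a much stricter criterion than a confidence interval for the difference, so a real excess could be passed over. If the tables are not by arm at all, no comparison is possible from them.

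**Working it through.** **The plan's own figure.** The safety section states no event rate, power or detectable difference, so there is no safety figure to reproduce.

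**Inputs.**
- Sample size: "We will enroll 700 participants" (protocol section 7.1), allocated 1:1 (section 2.5), so 700 / 2 = 350 per arm.
- Interval type: "exact binomial 95% two-sided confidence intervals" (SAP), taken as Clopper-Pearson.
- Control-arm AE rate p: not in the documents. Assumed range 1% to 10%, with a true doubling to 2p.
- Reading rule: not in the documents. Assumed here that intervals are shown by arm and harm is inferred when they do not overlap.

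**Formulas.** For x events in n = 350, the Clopper-Pearson limits are L(x) = the 2.5% quantile of Beta(x, n − x + 1) and U(x) = the 97.5% quantile of Beta(x + 1, n − x).

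- Overlap reading: sum Bin(x₁; 350, 2p) × Bin(x₀; 350, p) over all pairs with L(x₁) > U(x₀).
- Direct contrast: the same sum over pairs with z > 1.96, where z = [(x₁ − x₀)/n] / √[2p̄(1 − p̄)/n] and p̄ is the pooled proportion. This is the two-sided 5% chi-square test without continuity correction, counted in the direction of harm. Fisher's exact test was enumerated as a check.

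**Results: probability that a true doubling shows.**

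| Control rate to doubled rate | Intervals do not overlap | Chi-square contrast | Fisher's exact |
|---|---|---|---|
| 1% to 2% | 1.6% | 17% | 11% |
| 2% to 4% | 7% | 34% | 27% |
| 3% to 6% | 15% | 49% | 42% |
| 5% to 10% | 35% | 72% | 67% |
| 8% to 16% | 66% | 91% | 89% |
| 10% to 20% | 81% | 96% | 96% |

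The overlap reading reaches 50% at a control rate of about 6.4% and 80% at about 9.9%. The chi-square contrast does so at about 3.1% and 6.0%. With no true difference and a 5% rate in both arms, the overlap reading errs in about 0.3% of trials, not 5%.

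**Why the gap arises.** In normal approximation at 5% against 10%, the standard errors are √(0.05 × 0.95/350) = 1.165 points and √(0.10 × 0.90/350) = 1.604 points. Non-overlap needs an observed difference of about 1.96 × (1.165 + 1.604) = 5.4 points, more than the true 5. The contrast needs about 1.96 × √(1.165² + 1.604²) = 3.9 points.

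**Example.** With 18/350 against 36/350, the exact intervals are 3.1% to 8.0% and 7.3% to 14.0%, which overlap. The difference is 18/350 = 5.1 points, with standard error √(0.1029 × 0.8971/350 + 0.0514 × 0.9486/350) = 2.01 points and Wald 95% interval 5.1 ± 1.96 × 2.01, or 1.2 to 9.1 after rounding from the unrounded values. It excludes zero.

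**The case against.** The case against runs as follows.

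- **The placebo arm is used for safety elsewhere.** The DSMB compares AE incidence in both arms, and the Cox models compare death and outpatient hospitalization, which are also seriousness criteria. This stands: a reader might infer that the trial ignores its placebo arm for safety, and the documents do not support that. But DSMB review is monitoring during the trial with no stated method, and the Cox models do not reach hepatic, renal or muscle events. The Fisher sentence sits in a descriptive paragraph, names no AE and yields no effect estimate.
- **A doubling would not usually go unseen.** That stronger reading is tempting but depends on the event rate. Above about 6.4% in the control arm even the overlap reading shows a doubling more often than not, and common COVID-19 events may lie there. This stands.
- **At low rates the limit is sample size.** At 1% and 2% a direct chi-square contrast still misses a doubling in 83% and 66% of trials; 80% power would need 2,319 or 1,141 per arm. This stands too, though an estimated difference with its interval would at least show that uncertainty.
- **Overlap is not the SAP's rule.** Correct. The SAP sets no decision rule for AEs, so the calculation shows what is lost under one likely reading, not under a stated procedure.
- **The difference can be derived from by-arm counts.** True, if the counts are by arm. The safety section does not say they will be.

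**Conclusion.** The point holds for the SAP safety section: it promises no by-arm AE tables and no between-arm estimate, in a trial where disease and drug produce overlapping events and only the placebo contrast can tell them apart. It does not hold as a statement about the whole plan, nor as a general claim that a doubled AE rate would be missed.

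The size depends on assumptions the documents do not supply: the control rate, 350 evaluable participants per arm, by-arm intervals, and reading by overlap. Under these, a direct contrast is better at every rate in the table, and the gain is largest at about 3% to 8% (for example 35% to 72% at 5%). The primary efficacy analysis is unaffected. This is a change that should be made, not a threat to the trial's validity.

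**What to change.** In the SAP's Safety Analysis section, keep the population as all subjects and add a sentence such as:

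> The number and percentage of participants with any AE, any SAE, any AE leading to stopping of study drug, and any reported hepatic, renal or muscle event will be tabulated by arm, each with the risk difference (active minus placebo) and a 95% score-type confidence interval.

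The exact binomial intervals can stay as description of each arm. The sentence should be settled before unblinding, so that the safety method is not chosen with the results in view.

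The cost is a few more table columns, with no extra participants or data collection. One limit should be stated beside the tables. Appendix 2 schedules no follow-up laboratory tests, and section 8.2 says periodic monitoring does not apply to so short a treatment. The hepatic and renal contrasts will therefore rest on unscheduled clinical testing and on what is reported.
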